1.1. Synopsis

Protocol Title:

A Study to Evaluate Tirzepatide Concentrations in Breastmilk Following Administration of Single Dose of Tirzepatide by Subcutaneous Injection in Healthy Lactating Females

Brief Title: A Study to Measure Tirzepatide Levels in Breastmilk of Healthy Lactating Females

Regulatory Agency Identifier Number: IND: 128801

Rationale:

Tirzepatide (MOUNJAROTM; LY3298176) is a glucose-dependent insulinotropic peptide (GIP) and glucagon-like peptide 1 (GLP-1) receptor agonist approved as an adjunct to diet and exercise for improving glycemic control in adult patients with type 2 diabetes mellitus (T2DM). The disposition of tirzepatide for adult patients has been characterized but data is lacking on whether tirzepatide is excreted in breastmilk. There is a need to understand tirzepatide concentrations in breastmilk to better inform healthcare practitioners in managing women of childbearing potential who may be potential users of tirzepatide.

Study I8F-MC-GPIN (GPIN) is a postmarketing lactation study that will primarily assess the pharmacokinetics (PK) of tirzepatide in breastmilk following administration of a single **CCI** dose of tirzepatide via the subcutaneous (SC) route in healthy lactating females. Additionally, plasma PK of tirzepatide will also be assessed.

Objectives	Endpoints
Primary	
• To evaluate tirzepatide pharmacokinetics (PK) in breastmilk of healthy lactating females	 Area under the tirzepatide concentration-time curve in breastmilk from time 0 extrapolated to infinity AUC(0-∞)
Secondary	
• CCI	• CCI
• CCI	· CCI

Objectives and Endpoints:

Abbreviations: $AUC_{(0-tlast)}$ = area under the concentration versus time curve from time zero to the last observable concentration; C_{max} = maximum observed drug concentration; t_{max} = time to maximum observed drug concentration.

Overall Design

Brief Summary:

This is a postmarketing, open-label, single-treatment arm, single-dose, lactation study, assessing PK of tirzepatide in breastmilk and plasma in healthy lactating females.

Potential participants will be screened to assess their eligibility to enter the study within 27 days prior to Day -1. Participants will be admitted to the clinical research unit (CRU) on Day -1 to establish baseline measurements.

Participants will receive a single subcutaneous tirzepatide **CC** dose on Day 1 following overnight fasting of approximately 8 hours. Breastmilk and plasma samples will be collected. Participants will be permitted to leave the CRU on Day 5 following completion of study procedures. During inpatient stays, the infant is allowed to be in the CRU with the study participant during supervised visitation hours. On Days 6, 8, 15±1, and 22±1, participants may either return to the CRU for outpatient visits or have these visits be performed remotely by home health nurses as deemed appropriate by the study investigator. On Day 29±1, the participants will return to the CRU for the final follow-up visit.

Safety will be assessed by vital signs, electrocardiograms (ECGs), safety laboratory tests, and the recording of adverse events (AEs). Breastfeeding must be discontinued prior to the administration of tirzepatide and for the duration of the study.

Study Population:

Healthy lactating females.

Number of Participants:

Approximately 14 healthy lactating females will be enrolled so that about 8 females complete the study.

Intervention Groups and Duration:

Participants will receive a single SC tirzepatide CCI dose on Day 1.

The study duration for individual participants, inclusive of screening is expected to be approximately 8 weeks, as detailed here:

- Screening: up to 27 days prior to Day -1
- Inpatient Treatment Period: Day -1 to Day 5 (may be extended if necessary for safety reasons based on the Investigator's discretion)
 - Single dose of study intervention
- Outpatient follow-up period Days 6, 8, 15±1, and 22±1 with the final follow-up visit on Day 29±1.

Ethical Considerations of Benefit/Risk:

There is no anticipated therapeutic benefit for participants in this study.

As of 26 September 2022, tirzepatide was approved in the US, EU, and Japan as an adjunct to diet and exercise to improve glycemic control in adults with T2DM. Risks of tirzepatide have

been consistent with risks associated with other GLP-1 receptor agonists that are currently marketed. Potential risks include, but are not limited to, gastrointestinal effects, acute pancreatitis, increases in heart rate, and hypoglycemic events (GLP-1 receptor agonist class effect), which are all monitorable.

No clinically significant safety or tolerability concerns have been identified during clinical investigation of tirzepatide up to the single dose of 5 mg or multiple weekly doses up to 15 mg, attained by stepwise dose escalation. The maximum tolerated dose as a single dose of tirzepatide in healthy participants was determined to be 5 mg (Coskun et al. 2018). Based on this information, the single dose of **CO** tirzepatide to be administered in this study is anticipated to be tolerable in healthy lactating females.

Tirzepatide is a peptide molecule that is administered subcutaneously. Its excretion into the breastmilk is expected to be low. Even if it is ingested orally by a breastfed infant, it is unlikely that the tirzepatide peptide will be absorbed intact, since it will be digested in the gastrointestinal tract. Despite this, breastfeeding to infant will be discontinued and prohibited for the duration of the study to avoid exposing the infant to tirzepatide.

The participation in the study requires interruption of breastfeeding for a total of 29 days after the administration of a single dose of tirzepatide. Interruption of breastfeeding or lactation gap for such a period of time may lead to difficulty or even failure in achieving satisfactory relactation. This risk is expected to be partially mitigated by providing adequate relactation support and education to the study participants who wish to resume breastfeeding after the completion of the study. Thereby, a lactation consultant will be readily available at the CRU as a resource to support potential efforts to achieve relactation if required or requested by the participant.

Data Monitoring Committee: No

1.2. Schema

Procedure	Screening		Treatm	ent an	d Safety I	Monitor	ing		-			FU/EDa	Comments
Day	-28 to -2	-1	1	2	3	4	5	6	8	15±1	22±1	29±1	
Informed consent	Х												
Admission to CRU		Х											Enrollment will occur on Day -1
Discharge from CRU							X						May be extended at the investigator's clinical discretion for safety monitoring
Outpatient visits to CRU	Х							x	х	х	х	Х	Days 6, 8, 15±1, and 22±1 may be performed remotely by home health nurses
Review and confirm inclusion/exclusion criteria	Х												
Medical history and demographics	Х												
Physical exam/Medical assessment	Х	X				X			X			x	Screening: Full physical examination All other timepoints: symptom-driven
Height, weight, and BMI	Х	X							Х			Х	Height required only at screening
Temperature	Х		Р										
Safety 12-lead ECG	Х		Р			Х						X	
Vital signs	Х		Р			Х			Х			Х	

1.3. Schedule of Activities (SoA)

Clinical laboratory tests – local laboratory	х		Р						Х			Х	See Appendix 2 (Section 10.2) for details. Predose measures are for baseline purpose only and results need not be reviewed prior to tirzepatide dosing
Ethanol breath test and urine drug screen testing	Х	X											Per CRU local requirements
Pregnancy test	Х	X										Х	Screening: Serum pregnancy test. All other timepoints: urine pregnancy test
AEs/Concomitant Medications	Х	X	Х	Х	X	Х	x	X	X	X	X	Х	
Tirzepatide dosing			0										Actual tirzepatide dosing will be arbitrarily considered as time 0 hour
Tirzepatide plasma PK samples (h)			P, 12	24	48	72	96		168	Х		Х	Predose sample should be collected within 2 hours prior to dosing (time 0)
Glucose safety monitoring (h)			P, 12	24, 36	48	72							Performed using a glucometer using fingerprick capillary blood. Additional unscheduled

						measurements may be taken at the clinical discretion of the investigator

Abbreviations: AE = adverse event; BMI = body mass index; CRU = clinical research unit; D = Day; ECG = electrocardiogram; ED = early discontinuation; FU = follow-up; h = hours; P = predose; PK = pharmacokinetics.

- Note: CRU should schedule procedures as appropriate. However, if multiple procedures take place at the same time point, the following order of the procedure should be considered in terms of prioritization: ECGs, vital signs, PK breastmilk samples, PK plasma samples, clinical laboratory samples, and glucose samples. Unless otherwise specified, predose samples and procedure may be collected or performed any time up to 24 hours prior to dosing.
- ^a Final follow-up will occur 28 days ± 1 day after tirzepatide dose. Early discontinuation visit should take place within 14 days upon confirmation of early discontinuation. Tirzepatide breastmilk and plasma PK samples need not be collected if the participant discontinues prior to receiving a dose of tirzepatide.
- ^b Optional breastmilk PK sample. Breastmilk PK sample may be collected based on participant's need to pump during this interval.

2. Introduction

2.1. Study Rationale

Tirzepatide (MOUNJARO[™]; LY3298176) is a glucose-dependent insulinotropic peptide (GIP) and glucagon-like peptide 1 (GLP-1) receptor agonist (RA) approved as an adjunct to diet and exercise for improving glycemic control in adult patients with type 2 diabetes mellitus (T2DM). The disposition of tirzepatide for adult patients has been characterized but data is lacking on whether tirzepatide is excreted in breastmilk. There is a need to understand tirzepatide concentrations in breastmilk to better inform healthcare practitioners in managing women of childbearing potential who may be potential users of tirzepatide.

Study I8F-MC-GPIN (GPIN) is a postmarketing lactation study that will primarily assess the pharmacokinetics (PK) of tirzepatide in breastmilk following administration of a single **CC** dose of tirzepatide via the subcutaneous (SC) route in healthy lactating females. Additionally, plasma PK of tirzepatide will also be assessed.

2.2. Background

Tirzepatide is a GIP and GLP-1 RA. It is a 39 amino acid synthetic modified peptide with agonist activity at both the GIP and GLP-1 receptors. Its structure is based on the GIP sequence and includes a C20 fatty di-acid moiety that prolongs the duration of action. It is administered once-weekly by SC injection in a single-use prefilled pen.

Tirzepatide has a chemical structure and pharmacologic profile that is distinct from GLP1 RAs due to the additional effects on GIP receptor (GIPR), which is unique compared to the marketed incretin mimetics. As an agonist, tirzepatide combines the signaling of each receptor for improved glycemic control (Coskun et al. 2018). By virtue of being an agonist incretin mimetic, tirzepatide has the potential of reaching higher efficacy in target tissues such as the insulin-producing pancreatic β -cells that express both GIPR and glucagon-like peptide 1 before reaching its therapeutic limitation, which supports its use as a treatment for T2DM.

Tirzepatide may attain additional efficacy by recruiting metabolically active tissues not targeted by classical GLP-1 analogs (for example, adipose tissue as indicated by the observation of increased energy utilization and resulting body weight loss) (Coskun et al. 2018; Frias et al. 2018). Weight loss data support the ongoing investigation of chronic weight management, non-alcoholic fatty liver disease, heart failure with preserved ejection fraction, obstructive sleep apnea, and chronic kidney disease as additional potential indications.

2.3. Benefit/Risk Assessment

There is no anticipated therapeutic benefit for participants in this study.

As of 26 September 2022, tirzepatide was approved in the US, EU, and Japan as an adjunct to diet and exercise to improve glycemic control in adults with T2DM. Risks of tirzepatide have been consistent with risks associated with other GLP-1 RA that are currently marketed. Potential risks include, but are not limited to, gastrointestinal effects, acute pancreatitis, increases in heart rate, and hypoglycemic events (GLP-1 receptor agonist class effect), which are all monitorable.

No clinically significant safety or tolerability concerns have been identified during clinical investigation of tirzepatide up to the single dose of 5 mg or multiple weekly doses up to 15 mg, attained by stepwise dose escalation. The maximum tolerated dose as a single dose of tirzepatide in healthy participants was determined to be 5 mg (Coskun et al. 2018). Based on this information, the single dose of **CC** tirzepatide to be administered in this study is anticipated to be tolerable in healthy lactating females.

Tirzepatide is a peptide molecule that is administered subcutaneously. Its excretion into the breastmilk is expected to be low. Even if it is ingested orally by a breastfed infant, it is unlikely that the tirzepatide peptide will be absorbed intact since it will be digested in the GI tract. Despite this, breastfeeding to the infant will be discontinued and prohibited for the duration of the study to avoid exposing the infant to tirzepatide.

The participation in the study requires interruption of breastfeeding for a total of 29 days after the administration of a single dose of tirzepatide. Interruption of breastfeeding or lactation gap for such a period of time may lead to difficulty or even failure in achieving satisfactory relactation. This risk is expected to be partially mitigated by providing adequate relactation support and education to the study participants who wish to resume breastfeeding after the completion of the study. Thereby, a lactation consultant will be readily available at the clinical research unit (CRU) as a resource to support potential efforts to achieve relactation if required or requested by the participant.

More information about the known and expected risks, serious adverse events (SAEs), and reasonably anticipated adverse events (AEs) of tirzepatide can be found in the package insert of MOUNJARO or in the tirzepatide Investigator's Brochure.

3. Objectives and Endpoints

Objectives	Endpoints
Primary	
• To evaluate tirzepatide pharmacokinetics (PK) in breastmilk of healthy lactating females	 Area under the tirzepatide concentration-time curve in breastmilk from time 0 extrapolated to infinity (AUC_{0-∞})
Secondary	
• CCI	· CCI
• CCI	· CCI

Abbreviations: $AUC_{(0-tlast)}$ = area under the concentration versus time curve from time zero to the last observable concentration; C_{max} = maximum observed drug concentration; t_{max} = time to maximum observed drug concentration.

4. Study Design

4.1. **Overall Design**

This is a postmarketing, single-site, open-label, single-treatment arm, single-dose, lactation study, assessing PK of tirzepatide in breastmilk and plasma in healthy lactating women.

Approximately 14 healthy lactating females will be enrolled so that about 8 females complete the study.

Participants will receive a single dose of tirzepatide CCI delivered by subcutaneous injection.

The study duration for individual participants, inclusive of screening, is expected to be approximately 8 weeks.

Screening

Screening may occur up to 27 days prior to Day -1. During the screening visit, participants will undergo screening tests as mentioned in Schedule of Activities (SoA; Section 1.3). Participants who are not enrolled within 28 days of screening may be subject to an additional medical assessment, clinical measurements or both, to confirm their eligibility. In such instances, at a minimum, the following screening tests and procedures should be repeated:

- weight
- vital signs
- safety 12-lead electrocardiogram (ECG)
- clinical laboratory tests, and
- pregnancy test.

Inpatient Treatment Period

Participants will be admitted to the CRU on Day -1 to establish baseline measurements.

Participants will receive a single SC tirzepatide CC dose on Day 1 following overnight fasting of approximately 8 hours. Participants will remain in the CRU until Day 5 following the completion of study procedures. During inpatient stays, the infant is allowed to be in the CRU with the study participant during supervised visitation hours. The inpatient stay for the participant may be extended at the clinical discretion of the investigator (for example, necessary for the participant's clinical wellbeing and management and monitoring of AEs).

Breastmilk and plasma samples for tirzepatide PK will be collected. Breastmilk volume will be measured across the study duration as indicated in the SoA. Safety will be assessed by physical examination, medical assessments or both, vital signs, ECGs, safety laboratory tests, glucose safety monitoring, and the recording of AEs. Breastfeeding must be discontinued prior to the administration of tirzepatide and for the duration of the study. All costs associated with formula feeding and breast pumps required during the study will be covered by the study sponsor.

Outpatient Follow-up Period

On Days 6, 8, 15±1, and 22±1, participants may either return to the CRU for outpatient visits or have these visits be performed remotely by home health nurses as deemed appropriate by the study investigator. On Day 29±1, the participants will return to the CRU for the final follow-up visit.

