5.1. Inclusion Criteria

Participants are eligible to be included in the study only if all of the following criteria apply:

Age

1. Participants must be greater than or equal to 18 years of age inclusive at the time of signing the informed consent.

Type of Participant and Disease Characteristics

- 2. Participants who are overtly healthy females as determined by medical evaluation including medical history, physical examination, and laboratory tests.
- 3. Female participants who delivered normal-term infant (at least 37 weeks gestation) and are at least 6 weeks postpartum at the time of screening.
- 4. Female participant who has well-established lactation and is breastfeeding her infant (1 supplemental bottle of formula per day is acceptable). Note: Breastfeeding must be discontinued prior to the administration of tirzepatide on Day 1 and not resumed for the remaining duration of the study until a follow-up visit (or for total of 29 days after tirzepatide dosing for participants who discontinue early).
- 5. Participants who have clinical laboratory test results, blood pressure, pulse rate, and an ECG reading that are considered to be within the normal reference range for the population or CRU or have results outside the normal reference range that are judged to be not clinically significant by the investigator at the time of screening.

Weight

6. Body mass index within the range of 18.5 to 40.0 kg/m², inclusive.

Sex and Contraceptive/Barrier Requirements

7. Females only.

Contraceptive use by participants should be consistent with local regulations regarding the methods of contraception for those participating in clinical studies. For the contraception requirements of this protocol, see Appendix 4 (Section 10.4).

Informed Consent

8. Capable of giving signed informed consent as described in Appendix 1 (Section 10.1), which includes compliance with the requirements and restrictions listed in the informed consent form (ICF) and in this protocol.

Other Inclusion Criteria

- 9. Have venous access sufficient to allow for blood sampling as per the protocol.
- 10. Having a breastfed infant who is able to feed from a bottle and use formula while breastfeeding is prohibited.
- 11. Agree to abstain from breastfeeding their infant from the dose of tirzepatide on Day 1 to the follow-up visit, or for a total of 29 days after tirzepatide dosing for participants who discontinue early, to avoid potentially exposing their infant to tirzepatide.

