7.2. Participant Discontinuation/Withdrawal from the Study

Discontinuation is expected to be uncommon. A participant may withdraw from the study

- at any time at the participant's request for any reason or without providing any reason
- at the discretion of the investigator for safety, behavioral, compliance, or administrative reasons
- if enrolled in any other clinical study involving an IP, or enrolled in any other type of medical research judged not to be scientifically or medically compatible with this study, and
- if the participant, for any reason, requires treatment with a therapeutic agent that is prohibited by the protocol and has been demonstrated to be effective for the treatment of the study indication. In this case, discontinuation from the study occurs prior to introduction of the new agent.

At the time of discontinuing from the study, if possible, the participant will complete procedures for an early discontinuation visit and posttreatment follow-up, if applicable, as shown in the SoA.

Note: Breastfeeding must be discontinued prior to the administration of tirzepatide on Day 1 and not resumed for the remaining duration of the study until a follow-up visit or for a total of 29 days after tirzepatide dosing for participants who discontinue early.

If the participant withdraws consent for disclosure of future information, the sponsor may retain and continue to use any data collected before such a withdrawal of consent. If a participant withdraws from the study, the participant may request the destruction of any samples taken and not tested, and the investigator must document this in the CRU study records.

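### Does the stated 29-day breastfeeding interruption conflict with a follow-up visit set at 28 ± 1 days after the dose?

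*Protocol*

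**What the plan says.** Three sets of statements bear on when a mother may resume breastfeeding.

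- **Narrative.** Sections 1.1 and 2.3 carry the same sentence: "The participation in the study requires interruption of breastfeeding for a total of 29 days after the administration of a single dose of tirzepatide". It makes no distinction between completers and others. It opens the paragraph on the risk that relactation may be difficult or fail.
- **Operative rule.** Section 4.1 states the general prohibition: "Breastfeeding must be discontinued prior to the administration of tirzepatide and for the duration of the study". Criterion 11 in Section 5.1 asks for abstention from the dose "to the follow-up visit, or for a total of 29 days after tirzepatide dosing for participants who discontinue early". Criterion 4 and the note in Section 7.2 say the same, for example "not resumed for the remaining duration of the study until a follow-up visit or for a total of 29 days after tirzepatide dosing", with the 29-day count again limited to those who discontinue early.
- **Visit timing.** Section 4.1 places the dose on Day 1 and says that on Day 29 ± 1 "the participants will return to the CRU for the final follow-up visit". Footnote a to the Schedule of Activities (Section 1.3) reads: "Final follow-up will occur 28 days ± 1 day after tirzepatide dose". The same footnote adds: "Early discontinuation visit should take place within 14 days upon confirmation of early discontinuation".

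**The concern.** The narrative states a fixed number of days after the dose, for everyone and without a tolerance. The release point for completers is a visit with a window, and most of that window falls before 29 elapsed days. A site could release a mother on Day 28, in line with criteria 4 and 11 and Section 7.2, and still not have met the 29 days in Sections 1.1 and 2.3. She could also resume a day or two before an early discontinuer who was dosed on the same date. The abstention exists to keep the infant from being exposed to tirzepatide, so a gap between its stated and its enforced length deserves a check. What mothers are told about the burden of taking part is also at stake.

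**Working it through.** **Inputs**

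- Dose on Day 1, taken as time 0 (Section 4.1; Schedule of Activities).
- Final follow-up on Day 29 ± 1, so Day 28, 29 or 30 (Sections 1.1 and 4.1).
- The same visit at 28 ± 1 days after the dose (footnote a).
- Stated interruption of 29 days after the dose (Sections 1.1 and 2.3).

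**Does the visit timing agree with itself?** Elapsed days = study day − 1. For Day 29, 29 − 1 = 28, and the window of ± 1 gives 27 to 29. This reproduces footnote a. The plasma sampling schedule counts the same way: Day 8 is labelled 168 h, and (8 − 1) × 24 = 168. The visit timing is consistent.

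**Does the visit deliver 29 days?** The documents do not say whether 29 is a study-day label or a count of elapsed days, so both readings are shown. The inclusive count treats Day 1 as the first day and therefore equals the study day.

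| Visit | Elapsed days (day − 1) | Short of 29 | Inclusive days | Short of 29 |
|---|---|---|---|---|
| Day 28 | 27 | 2 | 28 | 1 |
| Day 29 (nominal) | 28 | 1 | 29 | 0 |
| Day 30 | 29 | 0 | 30 | 0 (1 over) |

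The 29-day period for an early discontinuer ends on Day 1 + 29 = Day 30 by elapsed count, or on Day 29 by inclusive count. A completer seen on Day 28 is therefore released 2 days or 1 day earlier.

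**Which text governs conduct?** For completers, the general prohibition runs for the duration of the study, and criteria 4 and 11 and Section 7.2 end it at the follow-up visit. These statements agree with one another and with the schedule. For early discontinuers, a visit-based rule would not work, because footnote a lets their last visit follow soon after they discontinue, possibly well before Day 29. A count from the dose fills that gap. The protocol does not state this reason, but it is evident.

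**Does any analysis use the figure?** No. The SAP computes breastmilk parameters from the actual start time of each collection (Section 10.3.1), and the follow-up visit is the last one scheduled. The sample size is not based on a target precision (Protocol Section 9.5; SAP Section 8). The length of the interruption enters neither.

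**The case for a change.** The strongest opposing case is that no counting convention makes the whole permitted window satisfy 29 days. On the elapsed count, which the schedule itself uses, even the nominal visit is a day short. A tolerance of ± 1 day is ordinary for an assessment, but this visit also ends a precaution, and the narrative gives that precaution's length as a requirement. Criterion 11 links the abstention to infant exposure for both completers and early discontinuers, so the figure cannot be set aside as describing burden alone.

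The arithmetic stands in full. The inference that a safeguard has been undercut does not. In Sections 1.1 and 2.3 the exposure precaution comes in the paragraph before the quoted sentence, and its length there is the duration of the study. The 29-day sentence then describes the lactation gap. If the 27 or 28 elapsed days at an early or nominal visit are described as 29, the burden is slightly overstated, which is the cautious direction. Nothing in the documents shows that a 29-day threshold was set for completers and then relaxed.

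A site that compares the narrative with the criteria could still ask which one applies. It would find the answer for completers in Sections 5.1 and 7.2, where the release rule is written out. Whether the consent form repeats the 29 days cannot be checked, because those pages are not in the public copy.

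**Conclusion.** The mismatch is clerical, and no change to the plan follows. A nominal duration in the narrative differs from the visit-based release by 0 to 2 days if elapsed days are counted. On an inclusive count the only shortfall is 1 day, at the early edge of the window. Followed as written, the criteria and Section 7.2 give every participant a defined release point.

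The conclusion rests on two assumptions: that sites apply the eligibility and discontinuation text over the benefit/risk narrative, and that a difference about the size of the visit window does not matter for the infant. On the second, the documents show no harm. The protocol expects low excretion into milk and thinks intact absorption by the infant unlikely. Neither the breastmilk AUC nor the number of participants depends on the figure.

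The 29-day wording in Sections 1.1, 2.3, 5.1 and 7.2 and the visit timing in Sections 1.3 and 4.1 do not match to the day. Reconciling them is an editorial matter for whenever the text is next opened. The documents do not settle which length was meant, and no view on that is taken here.
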